For the above analyses, the variables of primary interest are the main effects of the interventions. *Session-level* covariate adjustment will include: (1) weekday of session, (2) dialysis session shift, (3) average session blood flow rate; (4) average session dialysate flow rate, and (5) dialysate composition (sodium, potassium, magnesium). *Patient-level* covariate adjustment will comprise: (1) patient demographics (age, race, ethnicity, sex, employment, literacy, education level, language spoken); (2) time since first dialysis; (3) cause of ESRD, (4) treatment history; (5) total transplants; (6) vascular access type; (7) patient laboratory data (serum phosphorous, dialysis adequacy, anemia management (hemoglobin), iron indices (serum ferritin, serum iron), mineral metabolism indices (calcium, phosphate, PTH)); (8) comorbidity index; (9) individual comorbidities and comorbidities in combination, including COVID-19; (10) patient's heart rate variability (based on variability in heart rate (HR) during dialysis session (difference between the highest and lowest heart rates, standard deviation of the heart rate measures, the square root of the mean squared differences of successive heart rate measures); (11) patient medications (prescriptions medications administered outside of center or in-center (including ESA prescription, iron, antibiotics and vitamin D analog), and non-in-center prescriptions). Patient data will be censored while they are at COVID-19 isolation facilities. Regression diagnostics will be used to assess model fit. Checks for functional form of continuous adjustment covariates will be carried out and any transformations will be implemented prior to adding the intervention variables to the model.

Three secondary analyses are planned for this Aim. The first will test the treatment effects in a similar model but adding adjustment for any covariates found to be unbalanced between treatment groups in preliminary analyses. This has the ability to further adjust for important confounders of treatment effects, but because it will use data-driven covariate decisions that are subject to analysis bias, it will be interpreted with caution. The next secondary analysis will test the interaction between the two interventions to detect a possible synergistic or antagonistic

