effect. (Further discussed in the heterogeneity of effects section). Although the study is not powered to detect even moderate interaction effects, it is possible that a strong interaction could be detected, and such an effect would be of interest.

The primary results will be based on the treatment effects tested in the initial models described for cluster-randomized trials with pre-planned covariates. Intent-to-treat analyses will be carried out, so that any deviations from the randomized interventions will not be taken into account in the primary test of treatment effects. Additionally, we will conduct as-treated analyses for the peer mentoring intervention whereby only patients who received peer mentoring are compared to patients in the other treatment arms, with adjustment for the same factors as in the intent-to-treat analyses. The small number of facilities (20) will preclude post-hoc adjustment for facility non-compliance with the interventions.

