With IRB waiver of consent and waiver HIPAA authorization with an opt out process, we expect that we will not have significant attrition due to patient withdrawal since interventions will be provided at the facility-wide level. Attrition may be seen in the patient activation (peer mentoring) intervention if patients choose not to participate in the peer mentoring program or if patients drop-out after starting the program. It is important to note that patients who drop out of the patient activation intervention will not be dropped from the overall study unless requested, and collection of outcome measures will continue. Any attrition (lack of participation in the

patient activation intervention) could contribute to a reduced estimate of treatment effect in analyses using the intent-to-treat principle; this reduction in estimated treatment effect would appropriately reflect the expected effect of this intervention in the general dialysis population.

A final type of attrition may be the possibility of missing data due to patients not completing the self-reported quality of life (KDQOL) survey or the patient symptom question regarding recovery time. For example, some participants may refuse to answer certain questions or may miss follow-up surveys. Where possible, we will note reasons for missing data by triangulating data sources to determine whether a patient has moved to another facility, or in accordance with two of our outcomes, been hospitalized or died (MD-4). Although every effort will be made to collect these data, some missing surveys are still likely, particularly among those in ill health. We do not expect missing surveys to be associated with study arm, but missingness itself can be analyzed for treatment differences as a tertiary outcome measure. The sample in each cross-section will include living patients only, so death will not be a problem as it would be in a longitudinal QOL study. We believe that this approach, along with our conservative assumptions regarding sessions needed as described previously, will largely prevent missing data for our primary outcome, as well as two secondary ones. Death will be tracked as an outcome, although the trial is not powered to assess this as a primary outcome. Data on subjects who leave the study site, will be used until their time departure from the study.

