We will compare the characteristics of those with missing data to those without missing data, to test whether characteristics are similar between the groups (see Preliminary Data Analysis) (MD-2). In addition to complete case analyses, we will use state-of-the-art statistical methods such as likelihood approaches and multiple imputation to deal with missing data (MD-3).¹⁶⁰ These sensitivity analyses will assess the robustness of the results to missing data (MD-5).

Heterogeneity of Treatment Effect Analyses (HT-2; Moderation). The primary analysis will examine average treatment effects (ATE), but we will also examine heterogeneity of treatment effects (HTE) on HD session instability (IDH) rate for a variety of covariates, particularly those that are characterized by differential outcomes among HD patients (HT-1). Covariates of interest for HTE analyses include: age, race,¹⁶³, ethnicity, level of education¹⁶⁴, literacy, presence of comorbidities, and heart rate variability (HT-4). Supporting these HTE analyses, greater benefits from peer mentoring for African Americans were found in a trial conducted by our advisory partner, NKFM.¹⁸ Depending on sample sizes obtained for each of the covariates of interest, either a subgroup analysis or an analysis including interaction terms will be employed to examine HTE (HT-3). Only two-way interactions between the treatment indicator and each of the covariates will be analyzed. There may be different moderators for the two interventions.

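### The primary model adjusts for about two dozen routine-record covariates but has no rule for a missing one, so otherwise eligible patients with incomplete records would drop out of the main result

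*Combined protocol and SAP*

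**What the plan says.** Section 11.4 (Analysis of Primary Outcome) computes each patient's proportion of unstable sessions among those with at least 60 sessions and fits a linear mixed model in the SAS MIXED procedure with a random effect for facility. The adjusted model carries the main result: "The primary results will be based on the treatment effects tested in the initial models described for cluster-randomized trials with pre-planned covariates".

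The patient-level list for that model is long. It opens with "patient demographics (age, race, ethnicity, sex, employment, literacy, education level, language spoken" and goes on through dialysis history, vascular access, laboratory values such as "iron indices (serum ferritin, serum iron), mineral metabolism indices (calcium, phosphate, PTH", a comorbidity index, "individual comorbidities and comorbidities in combination, including COVID-19", heart rate variability and medications.

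Under Missing Data Issues, the same section discusses facility drop-out, patient withdrawal and survey non-response ("A final type of attrition may be the possibility of missing data due to patients not completing the self-reported quality of life (KDQOL) survey"). It then plans to compare patients with and without missing data and states: "In addition to complete case analyses, we will use state-of-the-art statistical methods such as likelihood approaches and multiple imputation to deal with missing data". The next sentence gives these methods their status: "These sensitivity analyses will assess the robustness of the results to missing data". Section 5.4.3 repeats this text. Neither section mentions a missing covariate.

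**The concern.** A mixed model fitted by likelihood copes with missing outcomes but not with missing predictors. MIXED omits any record with a blank covariate. With this many covariates, small gaps in each can add up to a large number of excluded patients.

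Gaps are plausible. Section 15.3 takes the covariates from the electronic health record, and section 8.1 adds only two questions to usual care (recovery time and fluid-goal requests), neither of which is a covariate. Literacy, education and employment therefore depend on what clinics happen to record.

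At stake is who the primary result describes. Section 2.2.2 includes all non-vulnerable patients to counter selection bias, and section 14.3 supports the consent waiver by arguing that participation must be nearly complete. Silent deletion for an empty field works against that aim. Section 11.2 makes no allowance for it in its 60 patients per facility.

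**Working it through.** **1. Number of patient-level covariates (section 11.4).** Demographics 8; time since first dialysis, cause of ESRD, treatment history, transplants and vascular access 5; laboratory entries 8 (phosphorous, adequacy, hemoglobin, ferritin, iron, calcium, phosphate, PTH), or 7 if phosphorous and phosphate are the same test; comorbidity entries 2; heart rate variability 1; medications 1. Total 8 + 5 + 8 + 2 + 1 + 1 = 25, or 24. Counting comorbidities and drugs singly would give more.

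**2. Reproducing Table 5 (section 11.2).** Inputs: 10 facilities per group, m = 60 patients per facility, ICC 0.10, alpha 0.05 (taken as two-sided, which reproduces the table). Effective n per group = 10m/(1 + (m − 1) × 0.10) = 600/6.9 = 87.0. Power = Φ(D/(SD × √(2/87.0)) − 1.96). For D = 0.034 and SD = 0.08 this is Φ(2.80 − 1.96) = 80.0%. The other three columns give 61.1%, 90.9% and 80.9%, against the stated 61%, 91% and 81%. The table is reproduced.

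**3. Share of patients lost.** The documents give no missingness rate, so r, the rate per field, is an assumption. If gaps are independent across 24 fields, the loss is 1 − (1 − r)^24. If the same patients lack every field, the loss is r. Power uses the formula in step 2 with the reduced m (D = 0.034, SD = 0.08).

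| r per field | Loss, full overlap | Loss, independent | Patients per clinic, independent | Power, independent |
|---|---|---|---|---|
| 1% | 1% | 1 − 0.99^24 = 21% | 60 × 0.786 = 47 | 78.6% |
| 2% | 2% | 1 − 0.98^24 = 38% | 60 × 0.616 = 37 | 76.9% |
| 3% | 3% | 1 − 0.97^24 = 52% | 60 × 0.481 = 29 | about 75% |

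At 36 patients per clinic the effective n is 360/4.5 = 80 and power is 76.7%. With 25 fields the independent losses become 22%, 40% and 53%.

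**4. Gaps confined to a few fields.** If only literacy, education and employment had gaps, independently at 5% each, the loss would be 1 − 0.95^3 = 14%.

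**5. Two readings of the missing-data sentence.** If complete case is the base analysis, deletion is the stated method. If complete case is only one of several sensitivity analyses, the primary model has no rule, and the named procedure deletes by default. The consequence is the same. The planned multiple imputation does not change the primary result on either reading, because it is labelled sensitivity, and the plan does not say whether it covers covariates.

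**The case against.** The strongest reply is that the plan never says the primary model is complete-case. The sentence follows a discussion of survey non-response and may simply list several approaches. That is fair: complete case as the base run is a strong inference, not an explicit statement. Step 5 shows why it does not remove the problem.

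A reader might also infer a contradiction with intent-to-treat. The documents do not support this. Section 11.4 defines the term by departures from assignment ("so that any deviations from the randomized interventions will not be taken into account in the primary test of treatment effects") and says nothing about covariate completeness. Likewise, section 14.3 argues for waiving consent and does not set an analysis rule. The tension is with the protocol's aim, not its wording.

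A reader might blame covariate deletion for the loss of newcomers and patients with thin records. Much of that loss comes from a separate rule: 60 sessions is about 20 weeks at three per week, so many late entrants are already out of the primary analysis. Patients who remain have had months in which laboratory values could be recorded. The plan sets no laboratory window or averaging rule, so one missed draw need not exclude anyone; what matters is having no usable value.

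The size is also uncertain. Independence across all fields is close to the high-loss extreme, and the fields are not equally prone to gaps. Age and sex are probably near complete, and an absent comorbidity code would probably be read as no comorbidity. The attached Data Elements List, which may define these fields, is not among the documents available here. Finally, the planned comparison of patients with and without missing data would help to reveal selection, though it would not put anyone back into the primary result.

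**Conclusion.** The point holds as a gap in the primary method. The adjusted model is the headline analysis, it carries about 24 to 25 patient-level covariates from routine records, and no rule covers a missing one. Fitted as written, it would rest on those patients with at least 60 sessions whose covariates are all usable.

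The size is not known. At an assumed 1–3% missing per field the loss lies between 1–3% and 21–52%, depending on overlap. It would be wrong to read the upper figures as a forecast that a fifth to a half of patients will be lost, because nothing in the documents gives a rate or supports independence. Over this range, power for the 0.034 difference falls from 80% to no lower than about 75%, because variation between clinics dominates. The main cost is a primary estimate selected by completeness of the record.

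**What to change.** State in the covariate and missing-data paragraphs of section 11.4 that the primary model keeps every otherwise eligible patient. Take covariates from before the intervention or, for patients who join later, at clinic entry. This timing has to be written in, because the present list is not limited to pre-intervention values and includes within-session heart rate variability and medications. Section 5.4.1 also expects 15–20% of patients to be replaced during the study, so a rule based only on the pre-intervention period would itself create gaps.

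Name one method in advance, applied blind to arm: single imputation with a missing indicator, or multiple imputation that respects facility clustering. Define what counts as a usable laboratory value. Make complete case a sensitivity analysis, and keep the planned multiple imputation in general form rather than confining it to KDQOL and recovery time.

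The cost is a few lines of plan and code, a little more programming and one prespecified imputation choice. No new data are needed.

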In both Aims 1 and 2, the primary results will be based on the treatment effects tested in the initial models described for CRCTs with pre-planned covariates. Depending on the specific outcome, covariate adjustment for these analyses will include: (1) patient demographics (age, race, ethnicity, sex, employment, literacy, education level, language spoken), (2) time since first dialysis, (3) cause of ESRD, (4) treatment history, (5) total transplants, (6) vascular access type, (7) patient laboratory data (serum phosphorous, dialysis adequacy, anemia management (hemoglobin), iron indices (ferritin, serum Iron), mineral metabolism indices (calcium, phosphate, PTH)); (8) comorbidity index; (9) individual comorbidities and comorbidities in combination, including COVID-19; (10) patient's heart rate variability for the whole session or up until IDH occurs (if IDH occurs) (based on variability in heart rate (HR) during dialysis session (Difference between the highest and lowest heart rates, standard deviation of the heart rate measures, the square root of the mean squared differences of successive heart rate measures)); and (11) patient medications (prescriptions medications administered outside of center or in-center (including ESA prescription, iron, antibiotics and vitamin D analog)). Intent-to-treat analyses will be carried out, which means that any deviations from the randomized interventions will not be taken into account in the primary test of treatment effects. Additionally, we will conduct as-treated analyses for the peer mentoring intervention whereby only patients who received peer mentoring are compared to patients in the other treatment arms, with adjustment for the same factors as in the intent-to-treat analyses. The small number of facilities (20) will preclude post-hoc adjustment for facility non-compliance with the interventions.

Heterogeneity of Treatment Effect Analyses (Moderation). As with the primary outcome analyses, the following potential moderators will be assessed: 1) patient demographics, including age, race, ethnicity, literacy, and education level; (2) comorbidities; and (3) heart rate variability.

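### Effect heterogeneity may be examined by subgroup analysis in place of an interaction test, and the plan does not say how subgroup results would be compared

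*Combined protocol and SAP*

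**What the plan says.** The heterogeneity paragraph in section 11.4 (Aim 1) makes the average treatment effect primary and lists seven moderators of the effect on the IDH rate: age, race, ethnicity, education, literacy, "presence of comorbidities, and heart rate variability". The method is set by one sentence, which lets the numbers available for each covariate decide: "either a subgroup analysis or an analysis including interaction terms will be employed to examine HTE". No sample size is named at which one route gives way to the other. The paragraph then adds "Only two-way interactions between the treatment indicator and each of the covariates will be analyzed" and "There may be different moderators for the two interventions".

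For the secondary outcomes, the Aim 2 text in section 11.4 says "As with the primary outcome analyses, the following potential moderators will be assessed" and repeats the list without adding a method.

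Heart rate variability is defined only in the lists of adjustment covariates. For Aim 1 it is "based on variability in heart rate (HR) during dialysis session". The Aim 2 list adds that the measurement may run for the whole session or end when IDH occurs. The heterogeneity paragraph gives no measurement window for it as a moderator.

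**The concern.** Subgroup analysis is offered as an alternative to the interaction term, so for some moderators the plan may never estimate the difference in effects. The reader would then have two subgroup results and no stated way to compare them. The natural comparison, that one is significant and the other is not, is not a test of heterogeneity. It often occurs when the effects are equal, because each subgroup has less power than the whole trial and the subgroups may differ in size.

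What is at stake is a mistaken statement that some patients benefit more than others. The plan itself cites an earlier peer-mentoring trial with greater benefit in African Americans, so race-specific statements are a foreseeable output.

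Heart rate variability raises a separate point. If it is taken from sessions during the intervention, it follows randomization. If its window ends when IDH occurs, it also depends on the primary outcome.

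**Working it through.** **Inputs from section 11.2.** Difference D = 0.034 (range 0.034 to 0.043), SD = 0.08 (range 0.08 to 0.10), ICC = 0.10, 60 patients per facility, K = 10 facilities per group, alpha 0.05. Two-sided testing is stated for the secondary outcomes and reproduces Table 5.

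**Assumptions, not in the documents.** Subgroup splits of 50/50, 30/70 and 20/80, the same in every facility; a normal approximation; and no variation between facilities in the moderator's own effect.

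**Step 1: reproduce Table 5.** Design effect = 1 + 59 × 0.10 = 6.9. Effective n per group = 600/6.9 = 87.0. SE = 0.08 × √(2/87.0) = 0.01213. Power = Φ(0.034/0.01213 − 1.96) = Φ(0.84) = 80%. The other three cells give 61.1%, 90.9% and 80.9%, against 61%, 91% and 81% in the table. A t reference with 18 df would lower the four to about 75%, 56%, 88% and 77%.

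**Step 2: subgroup effects.** With m_s patients of a subgroup in each facility, the variance of the estimated effect is 2 × [ICC·SD²/K + (1 − ICC)·SD²/(K·m_s)]. The shared facility effect gives covariance 2·ICC·SD²/K = 2 × 0.00064/10 = 0.000128.

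- 50/50 (30 + 30): variance 2 × (0.000064 + 0.0000192) = 0.0001664 in each; correlation 0.000128/0.0001664 = 0.77; power 75% in each at D = 0.034.
- 30/70 (18 + 42): variances 0.000192 and 0.000155; correlation 0.74; power 69% and 78%.
- 20/80 (12 + 48): variances 0.000224 and 0.000152; correlation 0.69; power 62% and 79%.

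**Step 3: chance that exactly one subgroup has p < 0.05 when the true effect D is the same in both.** From the bivariate normal distribution with the moments above, SD = 0.08:

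| True D | 50/50 | 30/70 | 20/80 |
|---|---|---|---|
| 0 | 6.0% | 6.3% | 6.7% |
| 0.01 | 11.1% | 11.6% | 12.4% |
| 0.02 | 20.3% | 21.7% | 24.1% |
| 0.03 | 20.6% | 23.3% | 28.0% |
| 0.034 | 17.4% | 20.3% | 25.5% |
| 0.043 | 8.3% | 10.6% | 15.3% |
| 0.05 | 3.3% | 4.7% | 7.8% |

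With D = 0.043 and SD = 0.10 the three splits give 17%, 20% and 25%.

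**Step 4: the interaction test.** For a patient-level moderator the facility intercept cancels, so the variance of the difference in effects is 2·(1 − ICC)·SD²/K × (1/m₁ + 1/m₂).

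- 50/50: 0.001152 × (1/30 + 1/30) = 0.0000768, SE 0.00876. The difference detectable with 80% power is 2.80 × 0.00876 = 0.025.
- 20/80: 0.001152 × (1/12 + 1/48) = 0.00012, SE 0.01095, detectable difference 0.031.

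With SD = 0.10 the corresponding figures are 0.031 and 0.038. The false-positive rate is 5% for any common effect. A small subgroup shows as a wide interval and is no reason to leave out the term.

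**Step 5: multiplicity that remains.** Seven moderators by two interventions is at most 14 tests. If independent, the chance of at least one false positive is 1 − 0.95⁷ = 30% for seven and 1 − 0.95¹⁴ = 51% for 14.

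**The case against.** The strongest reply is that the plan does not commit the error. It mentions no p-values within subgroups and no rule for declaring heterogeneity from them. A subgroup analysis could mean estimates with intervals, and two-way treatment-by-covariate terms are already in the plan. This stands in part: a reader might infer that heterogeneity will be declared from subgroup p-values, but the documents do not say so. What remains is that the sentence on two-way terms limits the order of interactions without requiring one when the subgroup route is taken. The other interaction tests, in sections 4.1 and 11.4, are between the two interventions and do not cover patient moderators.

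A reader might also think that choosing the method after seeing sample sizes inflates error. Covariate counts are not outcome data, and initial analyses use coded arms (section 5.4.2), so the timing alone does no harm. The difficulty is the method that the rule allows.

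A third tempting step is to multiply up: 14 × 0.174 = 2.4 discordant pairs expected. That needs all seven moderators to take the subgroup route and both interventions to have a true 0.034 effect. The plan lets the route vary by covariate and the moderators differ by intervention. With no true effect the same product is 14 × 0.06 = 0.8.

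Finally, the definition of heart rate variability comes from the adjustment lists. On-treatment measurement of the moderator is therefore a possibility left open and not a stated plan.

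**Conclusion.** The concern holds as a gap in the stated method. The plan permits subgroup analysis instead of an interaction term and is silent on how subgroup results would be compared. If they were compared by significance, equal effects would look different in about 17% to 26% of trials at D = 0.034 and SD = 0.08. The rate is about 3% to 28% over true effects of 0 to 0.05, and depends on an unknown effect and on the assumed splits. At the largest effect with even or 30/70 splits it falls just below the 5% of the interaction test; elsewhere in the table it is higher.

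The reach is limited. Heterogeneity is secondary to the average effect, and the primary results come from the main-effect models, so the primary test is unaffected. This is a worthwhile improvement of the SAP and not a threat to the trial's main conclusion.

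**What to change.** Replace the either/or sentence in section 11.4 with one rule for both aims. For every listed moderator and each intervention, at any sample size, fit the treatment-by-moderator interaction in the model planned for that outcome (the mixed model for the primary outcome) and report its estimate and confidence interval. Give subgroup estimates from that model as description only. Label the whole set exploratory, since the interaction tests alone do not remove the multiplicity in Step 5.

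State that heart rate variability, when used as a moderator, is calculated from sessions before the intervention. Section 7.2 already provides a 12-week baseline, collected retrospectively at all clinics.

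The cost is small but not nil. Fewer subgroup findings will be nominally significant. Patients who enter during the intervention will lack baseline heart rate variability: section 5.4.1 expects 15% to 20% of patients to be replaced, and sections 4.1 and 7.2 allow entry until 8 weeks before the intervention ends. They would drop out of that one moderator analysis or need imputation, and the SAP should say which. No new data collection or extra patients are needed.
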